8 STATISTICAL CONSIDERATIONS

8.1 STATISTICAL ANALYSIS PLAN

Preliminary data analysis: One-way ANOVA will be used to compare demographic and baseline clinical characteristics across groups. **no missing data expected, SAS, p-value

Aim 1 Analysis: For the between-group analysis of functional connectivity, general linear model multivariate analysis of variance will be used with FC values between pairs of LSBN parcellations as dependent variables and group (DLB, AD, and CN) as a factor variable. Bonferroni post hoc test will be used to correct for multiple comparisons. The primary pairs of interest (see **Table 4**) based on available literature (see background and **Table 2**) will be analyzed first. Other combinations of these seven parcellations will be analyzed secondarily. If additional, unexpected anomalies are present between groups, we will test them in an exploratory fashion to advance this novel field of study.

Aim 2 Analysis: Pearson correlation analyses will be performed between functional connectivity values and neuropsychological test scores to evaluate the relationship between connectivity strengths and the clinical phenotype of DLB. Similar to Aim 1, we will focus on pre-specified pairs of interest, but will explore others if they present themselves in the functional connectivity analysis.

Table 4: Data Variables
Population Descriptors: age, sex, race, ethnicity, education, measures of baseline cognition (e.g. MoCA)
Aim 1: Evaluate the role of rs-fMRI and connectomic analysis as a biomarker of disease in DLB using data from an ADNI-2/3 population of MCI and mild AD subjects and a clinic population of DLB subjects
Group variable: DLB, AD, or CN

Dependent variables: Functional connectivity (FC) scores between pairs of LSBN parcellations
 
 • Primary pairs of interest (see background for justification of these choices): 
 ○ Locus coeruleus v. Basal nucleus of Meynert ○ Locus coeruleus v. Intralaminar nucleus of thalamus ○ Basal nucleus of Meynert v. Intralaminar nucleus of thalamus ○ PH v. FST ○ Substantia nigra v. Caudate nucleus • Exploratory pairs: Other 15 combinations of the pre-specified parcellations, other pairs of parcellations found to be anomalies by Infinitome program
Aim 2: Correlate cross-sectional dysfunction between LSBN parcellations with specific neuropsychological abnormalities in DLB Patients

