8.2 POWER ANALYSIS OR STATEMENT OF PRECISION

In a one-way ANOVA, sample sizes of 19 DLB, 38 AD, and 38 CN achieve 80% power to detect differences among the means versus the alternative of equal means using an F test with a 0.01 significance level and assuming a common standard deviation within a group of 0.05. This is true for any set of group means with a standard deviation greater than or equal to 0.02, which we anticipate being able to achieve based on previous research. All significant brain connection couples in Franciotti's work had standard deviations of the group means greater than 0.06.

For post-hoc tests, group sample sizes of 19 DLB, 38 AD, and 38 CN patients achieve 81% power to reject the null hypothesis of equal means when the population mean difference is 0.05 with a standard deviation for both groups of 0.05 and with a significance level (alpha) of 0.010 using a two-sided two-sample equal-variance t-test.

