06 FEB 2024

Aim 1

Our primary aim was to evaluate the role of rs-fMRI and connectomic analysis as a diagnostic imaging biomarker of disease for LSBN deterioration in DLB by comparing a clinical population of DLB patients with the ADNI 2/3 cohort of CN and AD/CI subjects. Specifically, we compared FC scores of prespecified parcellation pairs between the three groups using a one-way ANOVA. Eight parcellation pairs were chosen as the primary pairs, and twenty-two as the exploratory pairs.

Aim 2

Our secondary aim (aim 2) was to correlate cross-sectional dysfunction between LSBN parcellations with specific neuropsychological abnormalities in DLB patients. To accomplish this, we performed a two-stage analysis. First, we compared cognitive test scores between groups to understand which successfully distinguished between the cohorts. When possible, test scores were normed, i.e., converted to a Z- or T-score adjusted for age, sex, and years of education.

Primary Comparisons/A Priori Hypotheses:

- 1) *ADAS Number Cancellation Targets will be lower in DLB patients*
- 2) *Trails B time will be higher in DLB patients*
- 3) *Clock Drawing Tests will be lower in DLB patients*
- 4) *ADAS construction praxis score will be lower in DLB patients*
- 5) *Category Fluency Animals will be lower in AD patients*
- 6) *RAVLT recognition will be lower in AD patients*

The remaining comparisons were exploratory: Trails A time, RAVLT immediate recall, RAVLT delayed recall, Functional Activities Questionnaire (FAQ), Logical Memory Immediate, and Logical Memory Delayed. Digit Span Forward, Digit Span Backward, and Boston Naming Test were either missing or highly incomplete in ADNI controls; therefore, they were described in the DLB cohort only.

In the second part of the Aim 2 analysis, we correlated test scores with FC scores from the primary parcellation group in Aim 1, within diagnosis (DLB, CN, or AD/CI) and compared these correlations across diagnosis group. As above, we prespecified 4 hypotheses to test and consider the remaining correlations to be exploratory. Because of the high volume of statistical tests performed in the exploratory analysis, we used the Holm correction to adjust the p-values in the exploratory correlations only.

Primary/ A Priori Hypotheses:

- 1) *Caudate R / Substantia Nigra R and the Clock Drawing Test will be differently correlated for DLB patients vs other groups.*

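### Aim 1 calls FC a diagnostic biomarker for DLB, but the updated SAP states only a three-group ANOVA, does not carry the protocol's post hoc rules over to eight primary pairs, and no accuracy measure is planned

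*Combined protocol and SAP*

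**What the plan says.** The updated SAP (06 FEB 2024) sets Aim 1 as evaluating rs-fMRI connectomics "as a diagnostic imaging biomarker of disease for LSBN deterioration in DLB", with CN and AD/CI as comparators. The analysis is given in one sentence: "we compared FC scores of prespecified parcellation pairs between the three groups using a one-way ANOVA". It adds that "Eight parcellation pairs were chosen as the primary pairs", with twenty-two exploratory pairs. No Aim 1 significance level, correction across pairs or pairwise contrast is stated. Its one multiplicity rule is for Aim 2: "we used the Holm correction to adjust the p-values in the exploratory correlations only". Its one threshold, p < 0.15, also belongs to the exploratory Aim 2 correlations.

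The protocol says more. Section 8.1 states that "general linear model multivariate analysis of variance will be used with FC values between pairs of LSBN parcellations as dependent variables", and that "Bonferroni post hoc test will be used to correct for multiple comparisons", without saying whether the correction runs over groups, pairs or both. Section 3 lists five primary pairs. Section 8.2 powers a one-way ANOVA "using an F test with a 0.01 significance level". It then states that post hoc two-sample t-tests at 0.010 "achieve 81% power to reject the null hypothesis of equal means when the population mean difference is 0.05" with SD 0.05.

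The declared Aim 1 outcome is the FC score (1.1, 3). Sensitivity and specificity appear only in the background (2.1), for other imaging tests. The 3-sigma rule there describes the software and is not tied to any accuracy analysis.

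**The concern.** Three gaps bear on what a positive Aim 1 would mean.

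- **Which groups differ.** A significant three-group F means that the means are not all equal. It does not show whether DLB differs from AD, which is the harder diagnostic separation and the one on which section 2.1 reports conflicting connectivity results. The answer lies in the pairwise contrasts, and the update does not confirm them.
- **Error rate.** Primary pairs go from five to eight with no statement of which level or correction applies. Two analysts following the same documents could reach different Aim 1 conclusions.
- **Diagnosis versus difference.** A difference in means, even a real one, does not show how well FC separates individual patients. Section 2.1 says a diagnostic biomarker may affect medical decisions or trial enrolment, so the word carries weight.

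**Working it through.** **Inputs (8.2).** n = 19 DLB, 38 AD, 38 CN; within-group SD 0.05; alpha 0.01; post hoc difference 0.05. Five primary pairs in section 3, eight in the updated SAP.

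**Reproducing the plan's figures.**
- Post hoc t-test: d = 0.05/0.05 = 1; noncentrality 1/√(1/19 + 1/38) = 3.559; df 55; two-sided 0.01. Power is 80.9%, against 81% stated.
- Omnibus F: f = 0.02/0.05 = 0.4; λ = 95 × 0.4² = 15.2; df 2 and 92. Power is 82.0%, against 80% stated. Exactly 80% needs an SD of means of 0.0196, which rounds to the plan's 0.02, so this is rounding.

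**What F alone shows.** Let DLB = AD, with only CN shifted by δ. Then λ = [(57 × 38)/95] × (δ/0.05)² = 22.8 × (δ/0.05)². Power comes from noncentral F(2, 92) at 0.01; the contrast rows come from simulation (1,000,000 runs, pooled SD, F first and then each contrast at 0.01).

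| | δ = 0.04 | δ = 0.05 |
|---|---|---|
| λ | 14.59 | 22.8 |
| F rejects | 80% | 96% |
| F and DLB-AD contrast reject | 1% | 1% |
| F and DLB-CN contrast reject | 57% | 82% |
| F rejects, neither DLB contrast does | about 22% | 14% |

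So F will usually be significant here although DLB and AD do not differ. The contrasts keep the false DLB-AD finding at about 1%.

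**Error over eight pairs.** The documents state no family level and do not link 0.01 to five pairs. The arithmetic 0.05/5 = 0.01 is suggestive only.
- Five pairs at 0.01: at most 5 × 0.01 = 5%.
- Eight pairs at 0.01: at most 8 × 0.01 = 8%; if independent, 1 − 0.99⁸ = 7.7%.
- Under an assumed equal correlation between pairs of 0.3, 0.5 or 0.7, simulation gives about 7%, 6% or 5%.

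**What the powered difference means for accuracy.** With normal scores and equal SD, AUC = Φ(1/√2) = 0.760. The Hanley-McNeil SE for 19 v 38 is 0.072, so the 95% interval is 0.760 ± 1.96 × 0.072, about 0.62 to 0.90.

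**Power after a change.** DLB-AD difference 0.05, all on the pooled df of 92 so that the rows are comparable:

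| Level | No F gate | With F gate (range over where CN lies) |
|---|---|---|
| 0.01 | 82% | about 72-82% |
| 0.05/8 = 0.00625 | 77% | about 66-77% |
| 0.05/16 = 0.003125 | 70% | not needed |

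**The case against.** A reader might infer from the update that Aim 1 has no pairwise test and no error control at all. The documents do not support that. Sections 8.1 and 8.2 stand in the same combined document, with a Bonferroni post hoc test and t-tests powered at 0.01. If they apply, the DLB contrasts are made, and the 22% and 14% describe a misreading of F, not a prescribed procedure. What remains is that the update does not say they apply, and that the Bonferroni family was never defined.

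A reader might also infer that the update replaced a multivariate analysis with a weaker one. Section 8.2 already sized the study with a one-way ANOVA, so the mismatch with 8.1 predates the update.

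Nor do the figures show that the family error is now 8%. That is an upper bound, and the 5% target behind the comparison is an assumption. The protocol's primary pairs share parcellations, so positive correlation is plausible and would lower the rate. The inflation is modest.

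Finally, the protocol title speaks of a potential biomarker, the declared outcome is FC, and 19 DLB patients cannot settle accuracy. A group-difference study is a fair first step. This stands, and it is why rewording the aim is an acceptable alternative to adding AUCs.

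**Conclusion.** The point holds as a should-fix matter of specification and interpretation. The updated SAP keeps a diagnostic aim for DLB but states only an omnibus test. It does not say whether the protocol's post hoc rules apply to eight primary pairs, and no accuracy measure is planned in either document.

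Read alone, F can mislead substantially: up to 96% rejection in the cases examined with no DLB-AD difference. The multiplicity part is smaller, at most 3 points above an assumed 5%. The planned effect, if found, would correspond to only moderate separation.

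The F results rest on the plan's SD and sample sizes, and on normal data with equal variances. The AUC rests on normal scores with equal SD. None of this shows that the study's comparisons are invalid.

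**What to change.** 1. Base every Aim 1 conclusion about DLB on the DLB-AD and DLB-CN contrasts, and state the alpha and the family for eight pairs. If 5% is the target, two workable rules are:
   - within each pair, the F test and then the contrasts, each at 0.05/8 = 0.00625 (a closed procedure for three groups); or
   - no F gate, with Holm over the 2 × 8 = 16 DLB contrasts, first step 0.05/16 = 0.003125.

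   Ungated contrasts at 0.00625 would not suffice: two per pair give about 0.0113 under the global null, and 8 × 0.0113 is about 9%.
2. For each primary pair, report AUC with a 95% interval for DLB v AD and DLB v CN as descriptive estimates. State that DLB scans come from the local scanner (7.1.4) and the comparators from ADNI (4.1), so that AUC mixes disease with data source. Otherwise, describe Aim 1 as group differences instead of diagnostic evaluation.
3. The SAP is in the past tense. If the analysis has been run, label these additions post hoc.

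**Cost.** SAP wording and a few lines of analysis on existing FC scores. Power for a 0.05 DLB-AD difference falls by about 5 to 6 points within the gated procedure. Without the gate it falls from 82% to 70% at the first Holm step, which is the lower bound for Holm. The AUC intervals will be wide.

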1 PROTOCOL SUMMARY

1.1 SYNOPSIS

Title:	Connectomic Analysis in Dementia with Lewy Bodies: A Potential Diagnostic Imaging Biomarker
IRB Number:	A#_21-037_____
Study Description:	This is a cross-sectional study in patients with Lewy Body Dementia (DLB) with two comparison groups (AD and cognitively normal controls) drawn from a publicly available database called ADNI-2/3. We intend to study dysfunctional large scale brain networks (LSBNs) in DLB by comparing resting state functional MRI (rs-fMRI) imaging data. We propose using a novel cloud-based automated imaging software processing program that identifies abnormal brain networks or connectomes using rs-fMRI and data from the Human Connectome Project (HCP).
Specific Aims:	Specific Aim #1: Evaluate the role of rs-fMRI and connectomic analysis as a diagnostic imaging biomarker for LSBN deterioration in DLB by comparing a clinic population of DLB patients with pre-existing data from an ADNI 2/3 cohort of CN and MCI/mild AD subjects Specific Aim #2: Correlate cross-sectional dysfunction between LSBN parcellations with specific neuropsychological abnormalities in DLB patients
Outcomes:	Aim 1 Outcomes: Functional connectivity (FC) scores between pairs of LSBN parcellations. Aim 2 Outcomes: Functional connectivity (FC) scores between pairs of LSBN parcellations vs Neuropsychological test scores
Study Population:	Inclusions: 1) Age 40- 90 years, 2) Established DLB diagnosis (McKeith Criteria 2017), 3) MMSE>15 Exclusions: 1) Other forms of dementia including, but not limited to Alzheimer's dementia, frontotemporal dementia, vascular dementia, NPH, etc, 2) Inability to tolerate brain fMRI, 3) Risk of brain fMRI due to implants or metal. Sample Size: We plan to enroll 19 DLB patients. 38 AD and 38 CN age and sex-matched subjects will be selected from the ADNI-2/3 database.
Description of Sites/Facilities Enrolling Participants:	Participants will be enrolled at HealthPartners Neuroscience Center, located at [name].
Study Duration:	The duration of this study is 1.5 years.
Participant Duration:	Participants should take about 3 hours - total time for all the visits, that may be conducted within 6 weeks

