5.1 INCLUSION CRITERIA

In order to be eligible to participate in this study, an individual must meet all of the following criteria:

- Age 40- 90 years
- Established DLB diagnosis (McKeith et al. 2017)
- MMSE>15

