7 STUDY ASSESSMENTS AND PROCEDURES

7.1 STUDY ASSESSMENTS FOR ENROLLED PATIENTS

7.1.1 DEMOGRAPHICS AND MEDICAL HISTORY

Demographic information will be collected, including: gender, age, race, ethnicity, height, weight, BMI, education, dementia diagnosis, co-morbidities (such as Diabetes, Hypertension) and e-mail address for consent.

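### Aim 2 tests left un-normed are not adjusted for education between groups or for age within groups

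*Combined protocol and SAP*

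**What the plan says.** **Test scores.** The Updated A Priori SAP (06 FEB 2024), Aim 2, says: "When possible, test scores were normed, i.e., converted to a Z- or T-score adjusted for age, sex, and years of education". It does not name the normed tests or the norms used, and it does not say how the remaining tests are handled.

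**FC–cognition analysis.** For the second stage the SAP states: "we correlated test scores with FC scores from the primary parcellation group in Aim 1, within diagnosis (DLB, CN, or AD/CI". These correlations are then compared across diagnoses. Protocol Section 8.1 has the simpler form: "Pearson correlation analyses will be performed between functional connectivity values and neuropsychological test scores". Neither text mentions a partial correlation. The SAP's four primary hypotheses at this stage each say that a given correlation differs between DLB and the other groups. The other correlations are exploratory, Holm-adjusted, and judged at 0.15.

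**FC itself.** In the SAP, "we compared FC scores of prespecified parcellation pairs between the three groups using a one-way ANOVA". Section 8.1 uses a multivariate model with "group (DLB, AD, and CN) as a factor variable". No covariate appears in either.

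**Comparability of groups.** The Synopsis states that "38 AD and 38 CN age and sex-matched subjects will be selected from the ADNI-2/3 database", and Section 5.5 repeats the age and sex matching. Education is not a matching variable. It is collected, however: Section 7.1.1 lists "gender, age, race, ethnicity, height, weight, BMI, education". Section 8.1 compares demographics across groups, but no adjustment follows from that comparison. The DLB entry criterion in Section 5.1 is "Age 40- 90 years".

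**The concern.** By choosing norms adjusted for age, sex and education, the SAP treats these three variables as things to remove from a test score. It then removes them only where a norm exists. The six primary score comparisons may therefore mix adjusted and raw outcomes for a reason unrelated to the clinical question.

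Two separate paths stay open for a raw test:

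- **Between groups.** Matching deals with age and sex. It does nothing about education, so a difference in schooling between a clinic sample and ADNI volunteers would appear as a difference in cognition.
- **Within a group.** Matching balances age across groups but leaves the age spread inside each group. If older patients have both lower FC and lower scores, the two correlate without any direct link between them.

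At stake is whether a reported cognitive difference, or a reported FC–score correlation within a diagnosis, reflects disease or demographics.

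**Working it through.** **Inputs from the documents.** Planned group sizes are 19 DLB, 38 AD and 38 CN (Synopsis). Section 8.2 gives a post-hoc difference of 0.05, SD 0.05 and two-sided alpha 0.01. No power figure is given for Aim 2.

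**Assumed inputs.** The documents give no education gap, no correlation of age or education with any score, no correlation of age with FC, and no alpha for the primary Aim 2 tests. I assume a two-sided 5% level and show ranges for the rest.

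**1. The plan's own figure (Aim 1, used below only for cost).** Noncentrality = (0.05/0.05)/√(1/19 + 1/38) = 1/0.281 = 3.56. With 55 df and alpha 0.01, power is 80.9%. The stated 81% reproduces.

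**2. Education gap, un-normed test, DLB v one ADNI group.** Standardised shift = gap in SD × r(education, score). The rejection rate under no disease effect comes from the noncentral t, 19 v 38.

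- Gap 0.3 SD, r 0.3: shift 0.09 SD, error 6.1%.
- Gap 0.5 SD, r 0.3: shift 0.15 SD, error 8.2%.
- Gap 0.5 SD, r 0.5: shift 0.25 SD, error 14.1%.

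A wider grid runs from 5.4% (gap 0.25 SD, r 0.2) to 41.6% (gap 1.0 SD, r 0.5).

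**3. Shared ageing, un-normed test, one within-group correlation.** If FC and score are unrelated given age, the false correlation is r(age, FC) × r(age, score). By Fisher z, the rejection rate is 1 − Φ(1.96 − δ) + Φ(−1.96 − δ), with δ = atanh(r)·√(n − 3). Example: for r = 0.25 and n = 19, δ = 0.255 × 4 = 1.02, which gives 17.5%.

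| Age correlation with both | False r | Error, n=19 | Error, n=38 |
|---|---|---|---|
| 0.3 | 0.09 | 6.5% | 8.3% |
| 0.4 | 0.16 | 9.9% | 15.9% |
| 0.5 | 0.25 | 17.5% | 32.7% |

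Simulation agrees closely, and partialling out age brings the error back to about 5%. At an unadjusted 0.15 threshold the rates over the same range are 17.6%–34.5% (n=19) and 20.7%–53.0% (n=38). Holm would lower these.

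**4. Normed test.** On standardised variables, let b = r(age, score). Then cov(score − b·age, FC) = r(age, score)·r(age, FC) − b·r(age, FC) = 0. Removing linear age from the score alone closes the path. In simulation the correlation falls from 0.25 to 0.00 and the error is 4.8%–5.1%.

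**5. Difference between two correlations (form of the four primary hypotheses).** The statistic is [atanh(r₁) − atanh(r₂)]/√(1/16 + 1/35) for 19 v 38. With the same false r in both groups the numerator is zero and the error stays at 5.0%. If ageing acts only in DLB, a false r of 0.16 v 0 gives 8.3% and 0.25 v 0 gives 13.5%.

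**6. Cost of three covariates.** The correlation detectable with 80% power in 19 DLB patients goes from tanh(2.80/√16) = 0.60 to tanh(2.80/√13) = 0.65, with 19 − 2 − 3 = 14 residual df. The contrast in step 1 goes from 80.9% to 80.8% (df 55 to 52, assuming no variance gain and covariates unrelated to group).

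**The case against.** The case for leaving the plan alone is substantial, and much of it stands.

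- **Unadjusted FC.** A reader might infer that, because FC is never age-adjusted, every FC–score correlation is contaminated. Step 4 shows otherwise: adjusting one side is enough, provided the norm's age slope fits the group.
- **Primary correlation hypotheses.** A reader might carry the 7%–33% rates over to these. The rates belong to a test of one correlation against zero, whereas the primary hypotheses compare correlations between groups. A common ageing effect cancels there, and the documents give no evidence that it differs by diagnosis.
- **Exploratory rule.** The plan does not use an unadjusted 5% test for exploratory correlations. Holm lowers their rates. It does not remove the bias, because a confounded correlation is present in the data and only its cause is misread.
- **Unknown scope and assumed inputs.** The documents do not say which tests were left raw, and there may be few. The entry range of 40–90 years is an eligibility limit, not the observed age spread. Every correlation and gap above is assumed.
- **Norms are legitimate.** A reader might conclude that norms should give way to raw scores throughout. That is a choice between two sound methods, and the documents give no reason to discard the norms.

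What remains is a rule with no provision for un-normed tests, no education matching, and no covariate in any model.

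**Conclusion.** The point holds for un-normed tests, and adjustment there is a cheap improvement. As written, the plan leaves their group comparisons open to any education gap and their within-diagnosis FC correlations open to shared ageing.

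On the assumed inputs, the group comparisons run at 6%–14% error against a nominal 5% (shift 0.09–0.25 SD, 19 v 38). A single unadjusted within-group correlation runs at about 7%–18% at n=19 and 8%–33% at n=38 (age correlations 0.3–0.5 on both sides). Correctly normed tests are not affected. The four primary correlation hypotheses are affected only if the age-induced correlation differs between diagnoses.

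How many of the six primary score comparisons or four primary correlations involve a raw score cannot be determined from the documents.

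**What to change.** 1. List in the SAP which tests were normed, by which norms, and which were not.
2. **Stage 1.** For every un-normed test, replace the raw group comparison with a linear model of score on group, age, sex and education. Run the same model as a sensitivity analysis for normed tests.
3. **Stage 2, within diagnosis.** For un-normed tests, report partial correlations of FC and score given age, sex and education, again with a sensitivity analysis for normed tests.
4. **Stage 2, four primary hypotheses.** On the same footing, fit score on group, FC, group-by-FC interaction, age, sex and education, and test the interaction. This supplies the cross-group comparison that within-group partial correlations alone do not give. It compares slopes rather than correlations, so the SAP should say so.

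The SAP is written in the past tense. If the analyses have been run, the adjusted versions should be labelled with the date they were specified.

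The cost is SAP wording and a modest re-run. Age, sex and education are already among the population descriptors in Table 4, so no new data are needed. The statistical price is three degrees of freedom (detectable DLB correlation about 0.60 to 0.65) and, in the models across groups, an assumption of common covariate slopes in DLB, AD/CI and CN, which should be stated.

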5 STUDY POPULATION

For ADNI 2/3 data, we will include CN and AD subjects who have undergone rs-fMRI images (with DTI and T1 images) and have cognitive/function testing data available. Below we describe the study population regarding clinic recruitment.

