5.5 STRATEGIES FOR RECRUITMENT AND RETENTION

Recruitment: For Alzheimer's Disease Neuroimaging Initiative (ADNI), analysis will be based on data available from the database. As such there are no recruitment or retention activities. rs-fMRI data as well as variables listed in Table 3 & 4 will be downloaded from ADNI-2/3 for age/sex-matched mild AD (with supportive biomarkers) and age/sex-matched CN patients.

Clinic Population: Potential DLB subjects will be referred to the study coordinator by clinicians in the neurology departments of HealthPartners and Park Nicollet. Participants with clinic visits will meet with research staff. Other patients will be mailed/e-mailed a letter and flyer/brochure. An informed consent form will be provided to those individuals expressing interest in the study. A video or phone encounter will be arranged to provide additional details of the study and informed consent. This study will be listed as one of the regional DLB investigations on the Alzheimer's Association Trial Match website. All referrals will be directed to study staff who will contact interested participants by phone. Participation will include one virtual visit and two in-person visits at HealthPartners Neuroscience Center.

To reach our target enrollment, we anticipate that we will need to screen 40 people, of those 19 individuals will sign the informed consent.

Remuneration: Participants will be provided gift cards totaling \$100 per subject for completing certain visits of the research study. The gift cards will be provided at the end of the study for completing the cognitive and imaging visits.

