7.1.4 MRI IMAGING

Subjects will undergo MRI imaging at HealthPartners Neuroscience Center. Subjects will be screened for any contraindications for MRI. Subjects will undergo a protocol based on recommendation by Omniscent (o8t MR Acquisition Recommendations). We anticipate 15 minutes of scan run time using a 3T Siemens Skyra scanner and the following images will be obtained.

- 1) High-resolution multi-scan directional diffusion scan, which is most similar to a diffusion tensor image (DTI) acquisition - Specifically, diffusion weighted imaging with the following acquisition parameters will be used: *2 mm x 2 mm x 2 mm voxels, FOV = 25.6 cm, matrix = 128 mm x 128 mm, slice thickness = 2.0 mm, one non-zero b-value of b = 1000, 40 directions, and gap = 0.0 mm.*

- 2) EPI BOLD rs-fMRI - A resting-state fMRI as a T2-star EPI sequence, with 3 x 3 x 3-mm voxels, 128 volumes/run, a TE = 27ms, a TR = 2.8s, a field of view – 256mm, a flip angle = 90°
- 3) Anatomical Scan –T1 Weighting

All images will be de-identified and uploaded to the infinitome cloud-based server to be analyzed. Internal guidelines/best practices based on infinitome user manual will be developed for transfer, obtaining accounts, uploading of raw images and downloading of analyzed data.

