- 2) *Caudate R/ Substantia Nigra R and the ADAS Number Cancellation Targets will be differently correlated for DLB patients vs other groups.*
- 3) *FST R/PH R and the ADAS construction praxis will be differently correlated for DLB patients vs other groups.*
- 4) *FST R / PH R and the Clock Drawing Test will be differently correlated for DLB patients vs other groups.*

With respect to the exploratory correlations, we used a significance threshold of $p < 0.15$, which is an accepted approach for detecting effects in emerging research areas where it's preferable to err on the side of identifying novel effects versus failing to reject a null hypothesis when it is false (Type II error).

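### Does Aim 2 need spread and slope rules before a between-group difference in FC–test-score correlation can be reported?

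*Combined protocol and SAP*

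**What the plan says.** The Updated A Priori SAP gives Aim 2 the purpose to "correlate cross-sectional dysfunction between LSBN parcellations with specific neuropsychological abnormalities in DLB patients". Its second part computes correlations within DLB, CN and AD/CI, and then "compared these correlations across diagnosis group". Each of the four prespecified hypotheses names one parcellation pair and one test, and states that they "will be differently correlated for DLB patients vs other groups". The tests are Clock Drawing (twice), ADAS Number Cancellation and ADAS construction praxis. On scaling, the SAP says: "When possible, test scores were normed".

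The SAP names neither the coefficient nor the test. Protocol section 8.1 names the coefficient: "Pearson correlation analyses will be performed between functional connectivity values and neuropsychological test scores". That section gives the purpose as the relationship between connectivity and the clinical phenotype of DLB.

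The groups come from different sources. DLB patients enter with MMSE above 15 (section 5.1). The comparators are "age/sex-matched mild AD (with supportive biomarkers) and age/sex-matched CN patients" (section 5.5). DLB imaging is local: "We anticipate 15 minutes of scan run time using a 3T Siemens Skyra scanner" (section 7.1.4). For ADNI, "we will include CN and AD subjects who have undergone rs-fMRI images" (section 5). The only FC standard deviation in the documents is a common 0.05, assumed for the Aim 1 power statement in section 8.2.

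**The concern.** A correlation mixes three things: the slope, the within-group spread of both variables, and noise. If two groups share a slope but one has a narrower range of scores or noisier FC, its correlation is smaller.

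Such differences are plausible here. CN subjects are cognitively normal by definition, while DLB patients span a range of impairment. Matching covers age and sex only. Scans come from one local scanner for DLB and from existing images for the comparators, and harmonisation is stated for the cognitive tests only (section 4.2). Norming for age, sex and education does not equalise spread between diagnoses.

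At stake is how a positive result is read. A rejection could be presented as an FC–cognition relationship particular to DLB when only spread or scan noise differs. The plan does not require group SDs, floor or ceiling shares, or slopes for this part of Aim 2.

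**Working it through.** **The plan's own figure.** Section 8.2 states 81% power for 19 v 38, difference 0.05, SD 0.05, two-sided alpha 0.01. The noncentrality is 0.05 / [0.05 × √(1/19 + 1/38)] = 3.56 on 55 df, and power is 80.9%. The figure reproduces, but it concerns Aim 1 means. The documents give no power or effect size for the Aim 2 correlations.

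**Set-up for Aim 2.** The sizes 19 and 38 come from section 8.2. Assumed, because the documents do not give them: the Fisher z test, 5% two-sided, normal data, the DLB correlation r, and the ratio u of comparator to DLB score SD. With the same FC-on-score slope and residual SD in both groups, the comparator correlation is

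r_c = r·u / √(1 − r² + r²u²).

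The standard error is √(1/16 + 1/35) = 0.302. With d = (atanh r − atanh r_c) / 0.302, the rejection rate is Φ(d − 1.96) + Φ(−d − 1.96).

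**Worked case, r = 0.5, u = 0.5.** r_c = 0.25 / √(0.75 + 0.0625) = 0.277. d = (0.549 − 0.285) / 0.302 = 0.876. Rejection is Φ(−1.084) + Φ(−2.836) = 14.2% (14.8% by simulation, 40,000 runs).

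| r | u | r_c | Rejection, formula | Rejection, simulated |
|---|---|---|---|---|
| 0.3 | 0.75 | 0.230 | 5.7% | 5.9% |
| 0.3 | 0.5 | 0.155 | 8.0% | 8.0% |
| 0.3 | 1/3 | 0.104 | 10.4% | 11.0% |
| 0.5 | 1 | 0.500 | 5.0% | 4.9% |
| 0.5 | 0.75 | 0.397 | 7.1% | 7.4% |
| 0.5 | 0.5 | 0.277 | 14.2% | 14.8% |
| 0.5 | 1/3 | 0.189 | 22.0% | 23.2% |

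At stronger correlations the effect grows: at r = 0.6 and u = 0.5 the formula gives 19%, and at r = 0.7 it gives 26%.

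**Other mechanisms, simulated.**
- FC reliability 0.8 in DLB against 0.4 in the comparators gives 8–14% (latent correlation 0.5 to 0.7).
- A hard ceiling with half the comparators at maximum gives 5%, so no inflation. With 84% at maximum it gives 7–11%.

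**Would slopes settle it?** Not alone. With an equal FC-on-score slope and r = 0.5, a test of the score-on-FC slope rejects 29% at u = 0.5 and 45% at u = 1/3, more often than the correlation test.

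**Would a claim rule settle it?** Consider allowing a relationship claim after a rejection only if both SD ratios lie within 0.8 to 1.25, or if slope differences in both directions agree in sign with the correlation difference and their 95% intervals exclude zero.
- With equal SDs at 19 v 38, the observed SD ratio has a 95% range of 0.68 to 1.55 (square roots of the 2.5% and 97.5% points of F with 37 and 18 df). Both ratios fall inside the tolerance in only 52% of studies.
- With equal spread and correlations of 0.5 v 0, power falls from 46% to 38%.
- With the same score-on-FC slope and comparator residual SD halved, wrong claims under the rule are about 7% at r = 0.5, 12% at r = 0.6 and 20% at r = 0.7. At high r the score SD ratio stays near 0.8, so the tolerance lets many of these through.

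**The case for a change.** The strongest case for acting is that Aim 2 is meant to say something about the disease. Section 8.1 speaks of the relationship between connectivity and the clinical phenotype. The three tests in the correlation hypotheses are also ones on which the SAP predicts worse DLB performance, so a reader will want to know whether the groups also differ in range. Two imaging sources make unequal FC noise a real possibility. Extra tables and plots would use data already in hand and leave the four tests intact.

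Much of this stands. A rejection alone does not establish a different FC–cognition relationship, and group SDs, floor and ceiling shares, scatterplots and slopes with intervals would help a reader judge one. It does not follow that the plan is wrong.
- The hypotheses are worded as differences in correlation and promise neither a slope difference nor a DLB-specific mechanism.
- The SAP already compares the same scores and FC values between groups. SDs normally accompany such output, although no section requires them.
- The mechanism that the eligibility text points to most directly, CN subjects near ceiling, produces the least inflation.
- The larger rates need spread ratios of one half or less, or strong correlations, and no section supports those values.

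**Conclusion.** No change to the plan is needed. The four comparisons are valid for the hypotheses as written, and a rejection reported as a difference in correlations, with the comparator named, is a sound statement. Section 8.1 supplies the Pearson coefficient, and an analyst would sensibly use a standard comparison of independent correlations.

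The exposure is one of interpretation. For r = 0.3 to 0.5 it runs from none at equal spread, through 1 to 2 percentage points above 5% at a spread ratio of three quarters, to 8–15% rejection at one half. These figures assume normal data, Fisher z at two-sided 5% and the planned 19 v 38. The spread ratios, correlations and reliabilities are assumptions too, so the documents show a possibility and not an error.

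The formal remedy is at best a trade-off. Its tolerance is arbitrary and fails in about half of studies with equal SDs. It costs 8 points of power at 0.5 v 0, and it still passes 12–20% wrong claims at r = 0.6 to 0.7 when comparator residual SD is halved. What remains is good descriptive reporting, which analysts can add without altering any planned rule, number or test.
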